8.3 Notification, Recording, and Response to Seizure During TMS

Subjects will be given TMS treatment by a trained study nurse or TMS technician under the supervision of the study psychiatrist. In the event of a seizure during the TMS treatment, the modified DHMS seizure protocol will be followed. Treatment will be immediately halted, and the study Neurologist or consult resident will be paged. The seizure will be timed, and the Neurologist on call will determine whether treatment should be continued or if the patient should be withdrawn. A description of the event, including the time of the seizure and the response, as well as study personnel who were notified will be documented in REDcap under **Safety Reporting**.

Additional safety measures may be taken if the subject experiences seizures either during or after the TMS session. As indicated in Procedures, the patient will be accompanied by a proxy in the period between treatment days 1-2 and 2-3. The proxy will be given contact information for the on-call study neurologist, and educated about safety protocol in the event of a seizure. Depending on the participant's response to the TMS, the amount of treatment may be reduced on the subsequent day(s) or terminated altogether. This decision will be made by the study neurologist.

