Repetitive transcranial magnetic stimulation (TMS) is a nonpharmacological, noninvasive method for stimulating the brain and modulating neural network activity. TMS has shown potential benefit in treating a number of neuropsychiatric disorders, especially depression[39]. With TMS, an electromagnetic coil placed against the scalp is used to generate a rapidly changing, relatively high strength magnetic field (~2 Tesla) that passes unimpeded through scalp and skull and generates an electric current in the underlying cortex. Using current “figure of eight” coils, stimulation can be focused to a 2-3 cm diameter region of cortex, allowing relatively focused stimulation. Due to the rapid decrease in magnetic field strength with distance from the coil, stimulation is generally limited to surface cortical stimulation (e.g., sensorimotor cortices, surface prefrontal cortices). TMS has been investigated as a diagnostic and therapeutic approach for several neuropsychiatric conditions including depression, schizophrenia, obsessive-compulsive disorder, addiction, epilepsy, and parkinsonism.

High-frequency (HF) TMS refers to TMS delivered at a frequency at 5 Hz or above. HF TMS applied to the left dorsolateral prefrontal cortex (DLPFC) is an FDA-approved treatment for medication-resistant depression and is becoming widely available in the community. Left HF DLPFC TMS has established clinically and statistically significant antidepressant effects[40]. However, HF TMS can increase cortical excitability and is associated with an increased risk of seizure[41]. As such, use of FDA-approved depression treatment protocols in patients with epilepsy would be relatively contraindicated, and there has been reluctance to study TMS in patients with epilepsy. Despite this potential increased risk of seizures, at present time the actual risk of a patient with either focal or generalized epilepsy experiencing a seizure during the course of treatment with TMS has not been studied. In addition, there is no evidence to suggest that patient with focal epilepsy or generalized epilepsy differ with regards to the risk of potential seizures by high frequency TMS.

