Low-frequency (LF) TMS refers to TMS delivered at a frequency of 1 Hz or below. Unlike HF TMS, LF TMS can decrease cortical excitability and may have anticonvulsant effects[42]. Low frequency TMS applied to right DLPFC also has an extensive though smaller database supporting its antidepressant efficacy, and comparisons to left HF DLPFC TMS suggest both treatments work equally as well[43, 44]. Surprisingly, LF TMS has not been investigated as an antidepressant treatment in patients with epilepsy, though it would have clear advantages compared to HF TMS including increased tolerability and potentially anticonvulsant effects.

The mechanism of action of TMS is not fully known. As HF and LF TMS respectively increase and decrease cortical excitability of the underlying cortex, these local effects likely comprise some of the mechanism. Converging data strongly support a role for the dorsolateral prefrontal cortices in the pathophysiology of depression, and a common abnormal pattern is left-right imbalance in activity characterized by relatively lower left DLPFC activity (e.g., decreased blood flow or metabolism; increased alpha power) and relatively higher right DLPFC activity[30, 45-49]. A simple hypothesis is that TMS works by either “turning up” activity in the left DLPFC versus “turning down” activity in the right DLPFC. One measure of prefrontal cortical activity is alpha power derived from a resting state scalp EEG. Thus, patients with focal epilepsy and comorbid depression would be expected to have left-right asymmetry in prefrontal alpha power. Further, LF TMS to the right DLPFC would be expected to alter prefrontal alpha power asymmetry which may correlate with antidepressant efficacy associated with this intervention. As above, the effects of TMS on prefrontal theta power and prefrontal-temporal alpha coherence may also be involved in the antidepressant mechanisms of TMS.

1.3 *Preclinical Data*

No available non-clinical data is available.

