3.1 General Design

This protocol is for a pilot study designed primarily to assess whether patients with epilepsy can safely tolerate low-frequency transcranial magnetic stimulation in an accelerated protocol to treat depression. We aim to enroll 20 patients with epilepsy and comorbid depression to receive a total of 14 hours of transcranial magnetic stimulation over 3 days at DHMC - Lebanon. We will assess safety of this protocol with regards to seizure frequency and other side effects of TMS treatment and the feasibility of using an accelerated protocol in this patient population. In addition to these primary aims, our secondary goal is to determine if dense array EEG can provide a useful biomarker for depression and its treatment in epilepsy. We will obtain a structural MRI before treatment and a dense array EEG before and after TMS treatment to assess for changes in specific dense array EEG based biomarkers. We will obtain a function MRI before treatment, and a dense array EEG before and after TMS treatment. Subjects will complete a brief battery of neuropsychological testing

before and after the treatment to assess for any changes in social cognition or executive functioning that may result from TMS or the change in depressive symptoms.

In addition to recruiting patients, we will likewise recruit family members or friends of the patient and ask them to monitor the patient for side effects to TMS treatment. The recruited family member will bring the patient to the treatment and stay with the patient overnight at a local hotel and monitor for possible seizures or other adverse events of treatment. Family members will be instructed in seizure safety and be given emergency phone numbers to call if the patient is experiencing adverse effects of TMS. When feasible, patients and their family members will be given the option to commute to the medical center on treatment days rather than staying in a local hotel.

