3.2 Primary Study Endpoints

1. Change in weekly seizure rate as assessed by self-report seizure log.
2. Change in significant side effects as assessed by the Systematic Assessment for Treatment Emergent Events (SAFTEE)[50].
3. Feasibility of participation such that 80% of patients will complete the study protocol including all measures, MRI, dense array EEG, and TMS.
4. Correlation of pre and post TMS hemispheric frontal alpha power asymmetry, anterior cingulate theta power, and frontotemporal alpha coherence with changes in depression severity.

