5.1 Description

TMS Device

Repetitive transcranial magnetic stimulation (TMS) is a focal, nonpharmacological, noninvasive method for stimulating the brain and modulating neural network activity. To administer TMS, an electromagnetic coil is placed on the scalp, and uses electrical current to create magnetic fields that depolarize or hyperpolarize neurons in the brain. See attached manual for more information regarding the MagVenture TMS device.

TMS will be delivered at 1 Hz over the course of fifteen 50-minute trains, for a total of 45,000 pulses. Four trains will be planned for day 1, with no more than five trains occurring on day one. Seven trains will be planned for day two, and four trains will be planned for day three. No more than seven trains will be delivered on any one day, and the treatment will occur over no more than four days. If the fifteen trains are not completed by the end of the third treatment day, subjects will have the option of returning for a fourth day to complete the remaining trains. Stimulation intensity will be set to 80% of the individual's motor threshold (the lowest energy output of the machine needed to evoke a motor response in the small muscles of the left hand) for the first several stimuli of the first session. The intensity will be steadily increased in regular intervals during the first session until reaching 120%. If higher intensity stimuli are not tolerated (due to discomfort or misplacement of the stimulus), then treatment will be continued at a lower intensity until the following session. During the following session, stimulus intensity will again be sequentially increased to 120%.

Figure 1 MagVenture MagPro TMS device setup to provide left TMS treatment. This device is also capable of providing right TMS treatment as proposed in this study.

MRI

Magnetic resonance imaging (MRI) will be performed using a 3T Philips Intera Achieva scanner (Philips Medical Systems, Best, The Netherlands) with a 32-channel head coil. High-resolution anatomic images

will be acquired at $1 \times 1 \times 1.2 \text{ mm}^3$ resolution with an MPRAGE sequence (FOV $256 \times 240 \times 204 \text{ mm}^3$, TR shortest, TE shortest, FA 8° , SENSE factor 1). Patients will receive a resting, structural scan. Anatomical data will be used for EEG analyses as described below.

Dense Array EEG

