7.1 Statistical Methods

The study will be closely monitored for safety parameters with stopping rules as defined in Section 8.7. At the conclusion of the study, baseline demographics and clinical characteristics will be summarized with means, proportions and associated standard deviations. For safety, occurrence rates of SAE (seizures or hospitalizations) will be estimated and exact binomial confidence intervals will be formed. Very few if any are expected in this small study. The SAFTEE scale will be compared before and after TMS with independent t-tests based on the individual changes from baseline. The study completion rates will be estimated and compared to the target rate of 80% using exact tests for binomial data.

The secondary outcomes will be measured before and after treatment using dense-array EEG biomarkers and depression scores along with test results during functional MRI and EEG. Paired t-tests will be used to compare *change* in depression severity, memory, executive functioning, quality of life, and social cognition from baseline to endpoint. MRI patterns of activation will be analyzed. Analysis of variance for repeated measures will be used to test task and neuropsychological testing results.

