8.7 Stopping Rules

Study safety will be monitored by the co-PIs .The study will be stopped at if the following endpoints are reached:

1. If recruitment for the study is not feasible
 - a. no recruitment after 1 year
 - b. > 4 drop outs due to any reason (80% feasibility)
2. If TMS is deemed unsafe to patients with epilepsy

- a. > 3 patients with increase in baseline seizure frequency
- b. > 3 patients with significant worsening of depression
- c. > 3 patients with significant side effects of TMS other than seizures

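### The only named seizure endpoint is a weekly rate with no averaging window, and no planned analysis reports seizures during stimulation separately, although staff time and record them

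*Combined protocol and SAP*

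**What the plan says.** Section 3.2 names one seizure endpoint: "Change in weekly seizure rate as assessed by self-report seizure log". It gives neither a baseline window nor a follow-up window.

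Four other places also deal with seizures:

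- **Section 7.1** states that "occurrence rates of SAE (seizures or hospitalizations) will be estimated", with exact binomial intervals. It sets no time window and does not mention the session records.
- **Section 4.2.1** counts seizures within the 3-day course, as a rule for discontinuing an individual patient.
- **Section 8.3** requires a seizure during TMS to be timed and entered in the safety section of the electronic case report form: "A description of the event, including the time of the seizure and the response".
- **Section 8.7, rule 2a** is triggered by "> 3 patients with increase in baseline seizure frequency", again without a window.

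The seizure component of the SAE is described in three ways. Hypothesis 1.a in section 2 makes it an increase in seizure rate, 7.1 says seizures, and 8.1 gives a single seizure without admission as an example of a serious event.

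Section 1.2 says of low-frequency stimulation that "LF TMS can decrease cortical excitability and may have anticonvulsant effects".

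**The concern.** The primary aim is to learn whether patients with epilepsy can safely tolerate this stimulation. The most direct evidence is whether more seizures occur while the coil is running than the patient's own background rate predicts. The plan collects what that comparison needs (timed in-session events and a baseline seizure log) but never makes it.

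A weekly rate mixes a few hours of stimulation with days or weeks without it. If trains provoke seizures while the following weeks are quieter, the two effects pull the weekly rate in opposite directions. The named endpoint could then show little change or a fall, and no planned estimate would separate the two components.

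**Working it through.** **Stimulation time.** Section 5.1 states "TMS will be delivered at 1 Hz over the course of fifteen 50-minute trains, for a total of 45,000 pulses". Check: 15 x 50 x 60 s x 1 Hz = 45,000 pulses, so the figure reproduces. The duration is 15 x 50 / 60 = 12.5 h, and 12.5/168 = 7.4% of a week. Section 3.1 instead says patients "receive a total of 14 hours of transcranial magnetic stimulation over 3 days"; at 1 Hz that would be 14 x 3,600 = 50,400 pulses, and 14/168 = 8.3% of a week. The two passages must be reconciled. The steps below use 12.5 h.

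**Dilution.** If the hazard is k times background during trains and unchanged otherwise, the weekly rate over W weeks rises by (k - 1) x 12.5 / (168 x W). For k = 5:

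- W = 1: 50/168 = 29.8%
- W = 4: 50/672 = 7.4% (with 14 h: 56/672 = 8.3%)
- W = 26: 50/4,368 = 1.1%

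**Offset.** Over four weeks, 672 - 12.5 = 659.5 h are unstimulated. A fall of 50/659.5 = 7.6% in those hours cancels the five-fold excess completely. For one provoked seizure in a patient with 1 seizure per week, the cancelling fall is 1/W: 100% over 1 week, 25% over 4 and 3.8% over 26. The problem therefore depends on the window, which the plan does not give.

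**Does the SAE proportion help?** Under Hypothesis 1.a it is rate-based and inherits the dilution. Under the any-seizure reading it cannot be cancelled, but it saturates. Assume Poisson seizures and patient rates that follow a gamma distribution with shape 1 and mean m per week. The probability of at least one seizure in W weeks is then 1 - 1/(1 + mW). A five-fold hazard adds 50/168 = 0.298 week-equivalents to four weeks.

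| m per week | No TMS effect | Five-fold in trains |
|---|---|---|
| 2 | 1 - 1/9 = 89% | 1 - 1/9.60 = 90% |
| 1 | 1 - 1/5 = 80% | 1 - 1/5.30 = 81% |

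**Two analyses compared by simulation.** The assumptions are 20 patients, the rate model above, 4 weeks before TMS and 4 weeks from its start, and upper-tail 2.5% tests. The first analysis is a paired t-test on weekly rate. The second is a conditional test of in-train seizures against baseline seizures; under no effect, the in-train share is 12.5/(12.5 + 672) = 1.8%.

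| m per week | Hazard in trains | Weekly-rate test | In-train comparison |
|---|---|---|---|
| 2 | 5-fold | 7-8% | 97% |
| 1 | 5-fold | 5-6% | 81% |
| 0.5 | 5-fold | 4-5% | 54% |
| 0.25 | 5-fold | 4% | 29% |
| 2 | 3-fold | 4-5% | 67% |

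With no effect at 2 per week, the in-train comparison rejects in about 1.5% of trials, so its advantage does not come from excess false positives. If the period after the start of TMS is shortened to one week, the weekly-rate test at 2 per week (five-fold) reaches about 24%.

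**Why a baseline comparison is needed.** In 12.5 h, a patient with b seizures per week has at least one by chance with probability 1 - exp(-b x 12.5/168): 3.7% at 0.5, 7.2% at 1, 13.8% at 2 and 52.5% at 10 per week (the entry limit in 4.1). A raw in-train proportion cannot be interpreted without this background.

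**The case against.** A reader might infer that a weekly rate is the only seizure measure. It is not. Section 7.1 estimates SAE occurrence, 7.2 bases the precision for 20 patients on it, and 4.2.1 counts seizures within the course. Read literally, the 7.1 count includes a patient who seizes during a train, and later improvement cannot remove that patient.

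A reader might also infer that provoked seizures would go unseen. They would not: 8.3 halts treatment and records each one. In the 2-per-week, five-fold case the expected in-train hazard is 5 x 2 x 12.5/168 = 0.744, so 20 x 0.744/1.744 = 8.5 patients would seize during a train. With no effect it is 20 x 0.149/1.149 = 2.6. What is missing is the planned comparison between such figures.

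Three further points stand.

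- Section 7.1 names no test of weekly seizure rate, so the paired test above is illustrative and its 4-8% is not the power of the plan.
- Window and baseline rate are assumptions. A short window weakens the contrast, and so do rare seizures.
- The remark in 1.2 that the risk of a patient "experiencing a seizure during the course of treatment with TMS has not been studied" concerns a whole course, in a paragraph mainly about high-frequency TMS. It does not single out the train hours.

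Rule 2a has no window and could be applied to treatment days. The study monitoring plan (Attachment E) was not available to check. Neither point supplies an end-of-study estimate for stimulation time.

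**Conclusion.** The concern holds in this form: the only named seizure endpoint is a weekly rate without a window, no analysis in 7.1 isolates seizures during stimulation, and the SAE rate does not close the gap under either definition. The documents do not support the stronger claims that no other seizure measure exists or that in-session seizures would be hidden.

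In the illustrative case (five-fold hazard, four-week windows), detection is about 4-8% for a weekly-rate comparison and between 29% and 97% for the in-train comparison as the mean baseline goes from 0.25 to 2 seizures per week. These figures rest on Poisson seizures, gamma-distributed rates, complete delivery of 12.5 h and complete ascertainment. The size of the gain is uncertain, but its direction is the same at every baseline rate tried. This should be changed; it does not invalidate the trial.

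**What to change.** Amend 7.1 as follows.

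1. Report the number and proportion of treated patients with at least one seizure during a train, with an exact binomial interval. With 20 patients, the one-sided 90% upper limit is 0.109 for 0 events, 0.181 for 1 and 0.245 for 2.
2. Compare seizures during the train hours actually delivered with each patient's baseline rate times the same hours, for example by an exact conditional Poisson test stratified by patient. Add a sensitivity analysis over the window from the first train to 24 h after the last. State the baseline window.
3. Report the change in weekly rate during follow-up separately, over a stated window.
4. Name the sources: the 8.3 records and the log reviews at Visits 3 to 5.

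At the same time, reconcile the seizure-SAE definition across sections 2, 7.1 and 8.1, and the stimulation time between 3.1 and 5.1.

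The cost is SAP wording and a small analysis of data already recorded. The limitations should be stated: intervals are wide when baseline seizures are rare, an hourly baseline ignores time of day, and delivered hours depend on halts after a seizure.

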8.4 Recording of Adverse Events

At each contact with the subject, the investigator must seek information on adverse events by specific questioning and, as appropriate, by examination. Information on all adverse events should be recorded immediately in the source document, and also in the appropriate adverse event module of the case report form (CRF). All clearly related signs, symptoms, and abnormal diagnostic procedures results should be recorded in the source document, though should be grouped under one diagnosis.

All adverse events occurring during the study period must be recorded. The clinical course of each event should be followed until resolution, stabilization, or until it has been determined that the study treatment or participation is not the cause. Serious adverse events that are still ongoing at the end of the study period

must be followed up to determine the final outcome. Any serious adverse event that occurs after the study period and is considered to be possibly related to the study treatment or study participation should be recorded and reported immediately.

8.5 Reporting of Serious Adverse Events and Unanticipated Problems

Investigators and the protocol sponsor must conform to the adverse event reporting timelines, formats and requirements of the various entities to which they are responsible, but at a minimum those events that must be reported are those that are:

- related to study participation,
- unexpected, and
- serious or involve risks to subjects or others
(see definitions, section 8.1).

If the report is supplied as a narrative, the minimum necessary information to be provided at the time of the initial report includes:

 • Study identifier • Study Center • Subject number • A description of the event • Date of onset 	
 • Current status • Whether study treatment was discontinued • The reason why the event is classified as serious • Investigator assessment of the association between the event and study treatment
---	---

8.5.1 Investigator reporting: notifying the Dartmouth IRB

This section describes the requirements for safety reporting by investigators who are Dartmouth faculty, affiliated with a Dartmouth research site, or otherwise responsible for safety reporting to the Dartmouth IRB. The Dartmouth College IRB (CPHS) requires expedited reporting of those events related to study participation that are unforeseen and indicate that participants or others are at increased risk of harm. The Dartmouth IRB will not acknowledge safety reports or bulk adverse event submissions that do not meet the criteria outlined below. The Dartmouth IRB requires researchers to submit reports of the following problems within 10 working days from the time the investigator becomes aware of the event:

- Any adverse event (regardless of whether the event is serious or non-serious, on-site or off-site) that occurs any time during or after the research study, which in the opinion of the principal investigator is:

Unexpected (An event is “unexpected” when its specificity and severity are not accurately reflected in the protocol-related documents, such as the IRB-approved research protocol, any applicable investigator brochure, and the current IRB-approved informed consent document and other relevant sources of information, such as product labeling and package inserts.)

AND

Related to the research procedures (An event is “related to the research procedures” if in the opinion of the principal investigator or sponsor, the event was more likely than not to be caused by the research procedures.)

Reporting Process

Unanticipated problems posing risks to subjects or others as noted above will be reported to the Dartmouth IRB using the form: “Unanticipated Problems Posing Risks to Subjects or Others Including Reportable Adverse Events” or as a written report of the event (including a description of the event with information regarding its fulfillment of the above criteria, follow-up/resolution and need for revision to consent form and/or other study documentation).

Copies of each report and documentation of IRB notification and receipt will be kept in the Clinical Investigator’s study file.

Reporting Deaths: more rapid reporting requirements

Concerning deaths that occur during the course of a research study, the following describes the more rapid reporting requirement of the Dartmouth IRB for specific situations:

- Report the event within 24 hours when the death is unforeseen (unexpected) and indicates participants or others are at increased risk of harm.
- Report the event within 72 hours, for all other deaths, regardless of whether the death is related to study participation.

For reportable deaths, the initial submission to the Dartmouth IRB may be made by contacting the IRB Director or Associate Director. The AE/Unanticipated Problem Form is required as a follow up to the initial submission.

Other Reportable events:

For clinical drug trials, the following events are also reportable to the Dartmouth IRB:

- Any adverse experience that, even without detailed analysis, represents a serious unexpected adverse event that is rare in the absence of drug exposure (such as agranulocytosis, hepatic necrosis, Stevens-Johnson syndrome).
- Any adverse event that would cause the sponsor to modify the investigators brochure, protocol or informed consent form, or would prompt other action by the IRB to assure protection of human subjects.
- Information that indicates a change to the risks or potential benefits of the research, in terms of severity or frequency. For example:
 - An interim analysis indicates that participants have a lower rate of response to treatment than initially expected.
 - Safety monitoring indicates that a particular side effect is more severe, or more frequent than initially expected.
 - A paper is published from another study that shows that an arm of your research study is of no therapeutic value.
- Change in FDA safety labeling or withdrawal from marketing of a drug, device, or biologic used in a research protocol.
- Breach of confidentiality
- Change to the protocol taken without prior IRB review to eliminate apparent immediate hazard to a research participant.
- Incarceration of a participant when the research was not previously approved under Subpart C and the investigator believes it is in the best interest of the subject to remain on the study.
- Complaint of a participant when the complaint indicates unexpected risks or the complaint cannot be resolved by the research team.
- Protocol violation (meaning an accidental or unintentional deviation from the IRB approved protocol) that in the opinion of the investigator placed one or more participants at increased risk, or affects the rights or welfare of subjects.

